4.2 Method of Data Analysis

All data analyzed in this study will be administrative health and use data that is collected as part of routine medical care and record keeping. EPIC has offered to build the SQL queries required to produce the outcome datasets described in this protocol. Outcomes listed in Section 3.4. will be analyzed using regression analysis, including (a) a version with no covariates, (b) a version controlling for patient age/gender, race/ethnicity, A1c at baseline, days since most recent office visit at baseline, and doctor fixed effects. A flag identifying patients who are eventual participants of "Impact of Innovative Interventions on Diabetic Adherence with Digital Sensors" (a study recently submitted to the IRB that may have limited overlap with this population) will also be included in the controls. For outcomes indicating analysis of practice level treatment and control groups, standard errors will be clustered at the practice level.

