1.2 Hypotheses

1.2.1 Interfacing with primary care practices to encourage physicians to implement default online orders of blood glucose flowsheets and informational messaging for all patients with diabetes will increase patient adoption (as defined above).

1.2.2. Additional reminder messaging to patients that (1) emphasizes the value of tracking blood glucose data to the patient OR (2) emphasize the value of tracking blood glucose data to the doctor OR (3) informs patient of their selection for a chance to receive an award conditional on tracking will increase adoption relative to no reminder messaging.

1.2.3 Promotion of adoption of electronic blood glucose tracking through the means described above will result in the following intent-to-treat effects:

- (a) reduction in patient A1c
- (b) increases in frequency of doctor-patient interaction
- (c) changes to treatment plan path

1.2.4 Reminder messaging treatments that induce more intensive use of flowsheets will lead patients to experience larger effects as described in 1.2.3.

1.2.5 Entries of blood glucose data will be predictive of A1c on average and will lower over the study period.

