2.2 Setting/Location

Research will be conducted through the MyChart electronic medical records system with patients of Inova Health Systems primary care offices (27 locations). Half of the 27 primary care offices will be randomly selected to receive treatment, but outcome data (existing electronic medical records data) will be analyzed for the entire study population.

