2.3 Duration of Study

Primary care practices identified in the treatment group will be encouraged to place bulk orders for electronic glucose flowsheets over a period of two weeks. Patients will be actively encouraged to use flowsheets for 12 weeks following the administration period. Outcome data will be collected for a total of 38 weeks:

- (a) 12 weeks retrospective at baseline
- (b) 2 week administration period
- (c) 12 week implementation period
- (d) 12 week follow up period

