3.1.1 PRACTICE LEVEL PROMOTION

Providers in the randomly selected group of treatment primary care practices will be encouraged to batch order blood glucose flowsheets for all patients with diabetes with active MyChart accounts. The research team will contact physicians and practice managers with an explanation of the initiative and instructions for completing batch orders and viewing entries through the system. The practice will be advised to complete filling orders over a two week administration period, after which the implementation period will begin. A batch order will trigger two forms of alerts sent to providers, according to the default settings for electronic glucose flowsheets:

1. A bi-weekly report received of values that the patient has entered, or a notification that the patient has not entered data during the interval.
2. A notification when patient entered values are out of range (the patient also gets a notification that their doctor will see this value) according to the following current settings:

Notification Setting	Current Default
Pre-Meal Range (entry outside range=alert)	60-180 mg/dl
Post-Meal Range	100-240 mg/dl
Nighttime Range	60-300 mg/dl

Patients will automatically be notified when the flowsheet has been ordered for them. Additionally, providers will be given text for a secure smart-text message to send to all patients receiving the flowsheets, instructing them to enter data for the study period. The secure message will also provide them with information on how to enter data, and on the benefits of tracking blood glucose. Draft text of this message is included below:

Dear [Patient],

You may have seen that there is a new electronic form available for you to enter your blood glucose results in the MyChart portal. Keeping track of your blood glucose can help you manage your diabetes and reduce your chances for developing complications like heart disease, kidney damage and eye damage. As part of a new Inova program to help patients with diabetes get healthy, I would like you to try entering the results of your home blood glucose tests on MyChart for the next 3 months, through [Date]. Please let me know if you have any questions.

Sincerely,

[Practitioner]

WHAT TO DO NEXT

1. **Get help:** If you need help learning how to measure your blood glucose or getting testing supplies, you can contact [Practice Contact].

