3.4 Endpoints/Outcomes Measurements

Hypothesis: Interfacing with primary care practices to encourage physicians to implement default online orders of blood glucose flowsheets and informational messaging for all patients with diabetes will increase patient adoption.

Outcome Measures: Comparison of individuals between treatment and control practices-- (a) fraction of patients entering blood glucose measurements into MyChart flowsheets during implementation period & follow-up period (dichotomous), (b) mean number of flowsheet entries during implementation period and follow-up period (c) fraction of patients for whom order is placed by doctor

Hypothesis: Additional reminder messaging to patients that (1) emphasizes the value of tracking blood glucose data to the patient OR (2) emphasize the value of tracking blood glucose data to the doctor OR (3) informs patient of their selection for a chance to receive an award conditional on tracking will increase adoption relative to no reminder messaging.

Outcome Measure: Comparison of individuals across reminder messaging assignment groups (within treatment practices)-- (a) fraction of patients entering blood glucose measurements into MyChart flowsheets during implementation period & follow-up period (dichotomous), (b) mean number of flowsheet entries during implementation period and follow-up period

Hypothesis: Promotion of adoption of electronic blood glucose tracking through the means described above will result in the following intent-to-treat effects:

(a) reduction in patient A1c

Outcome Measures: Intent to treat comparison of individuals between treatment and control practices of the following measures at the end of the intervention period and follow-up period: (1) Mean A1c (2) Quartiles of A1c using quantile regression analysis (3) fraction of patients experiencing improvement [reduction] in A1c from baseline (dichotomous) (4) fraction of patients below benchmark 7.0% A1c (dichotomous)

(b) increase in frequency of doctor-patient interaction

Outcome Measures: Intent to treat comparison of individuals between treatment and control practices of the following measures during the intervention period and follow-up period: (1) number of securing messaging (2) number of phone interactions, and (3) number of in-office appointments

(c) changes to treatment plan path

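### A1c values come only from routine testing that the intervention may itself change, and the plan has no measurement window, no rule for untested patients and no comparison of testing by arm

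*Combined protocol and SAP*

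**What the plan says.** **Source of data.** Section 4.2 says everything analysed is "administrative health and use data that is collected as part of routine medical care and record keeping". Section 2.2 adds that "outcome data (existing electronic medical records data) will be analyzed for the entire study population".

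**Endpoints.** Section 3.4 promises an intent-to-treat comparison between treatment and control practices "at the end of the intervention period and follow-up period: (1) Mean A1c", followed by A1c quartiles, improvement from baseline and the share below 7.0%. All four need a recorded A1c. Section 2.3 sets 12-week implementation and follow-up periods and a baseline of "12 weeks retrospective at baseline". It does not say which test counts as the value at the end of a period.

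**Expected effect on contact.** Section 1.2.3(b) hypothesises "increases in frequency of doctor-patient interaction", and section 3.4 measures this partly by the "number of in-office appointments". Under section 3.1.1 a flowsheet order triggers "A notification when patient entered values are out of range" and a bi-weekly report, which also tells the provider when a patient has entered nothing.

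**Analysis.** Section 4.2 gives two regressions: (a) without covariates, and (b) with covariates that include baseline A1c, days since the last office visit and doctor fixed effects. It describes no missing-outcome method, no comparison of testing by arm and no sensitivity analysis. The A1c power calculation in section 4.1 counts all 7200 patients.

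**The concern.** A patient whom routine care does not test has no outcome value. If treatment practices see their patients more often, or react to out-of-range readings, they may order more A1c tests, and for a different mix of patients. Randomisation of practices protects a comparison of all patients. It does not protect a comparison among those who acquire a value after assignment.

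The observed means could then differ with no change in anyone's A1c. Extra tests in poorly controlled patients would mask a benefit, and extra tests in well-controlled patients would create one. Clustering the standard errors by practice leaves such a bias untouched. All four A1c endpoints are exposed.

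**Working it through.** **1. The plan's own figure.** Inputs from section 4.1: 7200 patients, 24 clusters (taken as 12 per arm with 300 patients each), SD 1.39, ICC 0.07, baseline correlation r = 0.80. Two-sided 5% alpha and 80% power are assumed, as neither is stated.

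- Design effect = 1 + 299 × 0.07 = 21.93.
- MDE = (2.074 + 0.858) × √[2 × 1.39² × 21.93 × (1 − 0.80²) / 3600] = 0.270, using t with 22 df. This reproduces the stated 0.27.
- Without the baseline factor (1 − 0.80²), the same formula gives 0.450.
- With half of the patients tested (150 per cluster), the adjusted MDE is 0.276. Missing tests cost little precision, so the issue is bias.

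**2. Raw shift with no true effect.** Assumed: A1c is normal with the mean of 6.74 and SD of 1.39 from section 4.1. In control practices 40%, 50% or 60% of patients at or below 7% are tested, and 10 points more above 7%. Treatment practices test 5, 10 or 15 points more, on one side of 7% only.

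- (7 − 6.74)/1.39 = 0.187, so 42.6% lie above 7% and 57.4% at or below. The group means are 8.02 and 5.79, a gap of 2.23.
- The share above 7% among those tested is w = 0.426·pH / (0.426·pH + 0.574·pL), where pH and pL are the testing rates above and at or below 7%.
- Shift = 2.23 × (w in treatment − w in control).
- Example at 40%/50%: control w = 0.213/(0.213 + 0.230) = 0.481. With 15 extra points above 7%, w = 0.547 and the shift is +0.146. With 15 extra points at or below 7%, w = 0.403 and the shift is −0.175.

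| Control testing (≤7% / >7%) | Extra above 7%: 5, 10, 15 points | Extra at or below 7%: 5, 10, 15 points |
|---|---|---|
| 40% / 50% | +0.053, +0.102, +0.146 | −0.065, −0.123, −0.175 |
| 50% / 60% | +0.045, +0.086, +0.124 | −0.053, −0.100, −0.144 |
| 60% / 70% | +0.038, +0.074, +0.108 | −0.044, −0.085, −0.122 |

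The absolute range is about 0.04 to 0.17.

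**3. Shift after adjustment for baseline A1c (patients with a baseline value).** Suppose testing depends on current A1c. A shift δ in the observed outcome mean then brings a shift of about r·δ in the baseline mean, and a regression slope of about r removes r²·δ. What remains is δ × (1 − 0.80²) = 0.36 δ.

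- Extra tests above 7%: 0.36 × 0.038 = 0.014 to 0.36 × 0.146 = 0.053.
- Extra tests at or below 7%: 0.36 × 0.044 = 0.016 to 0.36 × 0.175 = 0.063, with negative sign.
- A simulation under the same assumptions agrees. If testing depends on baseline A1c alone, the adjusted shift is essentially zero.

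**4. What to compare it with.**

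- Like for like: raw 0.04 to 0.17 against 0.45, and adjusted 0.01 to 0.06 against 0.27.
- Plausible signal: section 4.1 cites a 0.33 change from self-monitoring. Suppose it acts only through adoption. A 9.5 point rise (the stated detectable effect) gives 0.33 × 0.095 = 0.031. A rise from 2% to 20% (the two adoption rates assumed in 4.1) gives 0.33 × 0.18 = 0.059.
- False positives: with half tested, the adjusted standard error is about 0.094. A bias of 0.05 then raises a nominal 5% error rate to about 8%.

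**The case against.** Several points on the other side have force.

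- **The plan already adjusts.** Version (b) includes baseline A1c and days since the last visit, which removes most of the shift in these scenarios. This stands, with limits. Version (a) has equal standing in 4.2 and adjusts for nothing. Baseline A1c is itself a routine result, so limiting it to the 12-week look-back would drop further patients. Doctor fixed effects would absorb the practice-level treatment term if each doctor works in one practice, so (b) as written may not estimate this contrast.
- **A reader might set the raw shifts of up to 0.17 against 0.27 and infer a bias close to the detectable effect.** The documents do not support that, because 0.27 presupposes baseline adjustment.
- **A reader might infer that the plan restricts A1c to tested patients.** No section says so. It is an inference from routine data, no scheduled test and no imputation. A most-recent-value rule is not excluded.
- **The alert route is limited.** Alerts fire only on entered values. If every induced adopter above 7% who would otherwise go untested were tested, the extra would be 9.5 × 0.30 = 2.9 to 18 × 0.50 = 9.0 points. The 10 and 15 point scenarios above 7% need testing among patients who enter nothing. Non-entry reports and the initial message are possible routes, but their effect cannot be quantified.
- **Direction.** Alerts point mainly to poorly controlled patients, and so to masking a benefit. The text names no specific mechanism for the opposite, although a general rise in contact leaves it open.
- **A1c is downstream.** Section 1.1 makes the health analysis conditional on a significant rise in adoption. That limits when the issue arises, but does not remove it.

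**Conclusion.** The concern holds in bounded form. The documented defect is that A1c ascertainment is undefined and depends on routine testing, while the plan itself predicts more contact in one arm. Followed as written, it can yield a selection-biased contrast under an intent-to-treat label, most plainly in unadjusted version (a).

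Under the assumed testing rates and normality, the spurious difference is about 0.04 to 0.17 raw. Adjusted for baseline A1c at r = 0.80, among patients with a baseline value, it is about 0.01 to 0.06, or near zero if testing depends only on baseline A1c. The adjusted figure is small against 0.27, but about as large as the 0.03 to 0.06 that diluted adoption would produce. It therefore matters most for reading a small or null A1c result.

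The documents do not show that the bias will occur, how large it would be or which way it would go.

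**What to change.** Amend section 4.2 as follows.

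1. Define the A1c window for the end of the intervention period and of the follow-up period, and the rule for patients without a value in it.
2. Pre-specify the presence of any A1c result in the window as an outcome, compared by arm.
3. Base the A1c conclusion on a baseline-A1c-adjusted estimate rather than on version (a), in a form in which the practice-level treatment effect can be estimated.
4. Pre-specify as sensitivity analyses an inverse-probability-of-testing weighted estimate, with the testing model fitted separately by arm on baseline variables, and trimming bounds if testing differs by arm. The bounds are needed because weights built on baseline variables do not correct testing prompted by readings after randomisation. For the same reason the weighted estimate is better kept as a sensitivity analysis than made the main result.

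The cost is SAP wording and some extra analysis of records already being extracted. The bounds will be wide if testing differs by arm, and the weighting corrects only for measured predictors.

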1.3 Background and Significance

The percentage of the US population with diagnosed diabetes increased from 4% to over 7% from 1999 to 2014 (CDC 2016), with nearly \$1 in \$5 of health care dollars spent caring for people with diabetes (ADA 2013). There is substantial evidence that improved average blood sugar control (as measured by

A1c levels) is associated with significant decreases in the probability of complications from diabetes (ADA 2016). Commercially insured patients with type II diabetes who lower their A1c, blood pressure and lipid levels, experience significant reductions in total medical costs (Fitch et al 2013). Recent research also suggests that reduction in blood glucose variability is associated with reduced risk of complications and mortality independently of average blood glucose/A1c (Cavalot et al. 2006) (Sorkin et al. 2005).

For patients who are insulin-dependent, self monitoring of blood glucose (SMBG) is a critical aspect of disease management and regulation of blood glucose levels and variability. A landmark randomized controlled trial comparing intensive insulin therapy guided by frequent blood glucose monitoring to conventional insulin treatment. Intensive therapy delayed the onset and slowed the progression of diabetic retinopathy, nephropathy and neuropathy in patients with IDDM (Diabetes Control and Complications Trial Research Group 1993).

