However, for non-insulin dependent type 2 diabetics, there has been some debate over the value of self tracking. The ASIA randomized controlled trial of 689 patients over a period of 24 weeks found that patients assigned to perform 6 SMBG measurements per week had a statistically significant 0.3 reduction in A1c (ITT) after 6 months (Guerci et al 2001). However, the DiGem randomized trial found that SMBG without additional training had no effect on A1c after 1 year (Simon et al 2008). A Cochrane meta-analysis of 12 randomized controlled trials evaluating SMBG found a statistically significant mean reductions in A1c of 0.3 for studies with 6 month follow-up (effect sizes in individual studies ranged from .07 to .69), but no statistically significant change in A1c for studies with a 12 month follow up (Malanda et al 2012). However, the review was criticized for including few studies with 12 month follow-up (two, one of which had only 22 subjects). A more recent meta-study was updated to include the latest RCTs, finding a somewhat larger statistically significant reduction in A1c at 6 month follow-up (-.36), and a statistically significant reduction in A1c at 12 month follow-up (-.28) (Zhu et al 2016).

Potential sources of variation in effects of SMBG on A1c for insulin-naive patients across these studies include the characteristics of the patient population, differences in involvement of physicians and training/education provided to patients, as well as heterogeneity in adherence by patients. Much larger effects were found for newly diagnosed patients in comparison to those with a diagnosis greater than 1 year (-0.54 vs -.28 change in A1c). Some of the studies finding no effect of SMBG included mostly patient populations with already well-controlled A1c. Both meta-studies pooled interventions with different levels of guidance and structure to glucose testing.

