Two key factors in enhancing the effectiveness of SMBG seem to be patient adherence and physician involvement (Clark 2007). In one study, structured SMBG was compared to enhanced standard care for 483 poorly controlled insulin-naive type 2 diabetics (Polonsky 2011). Analysis revealed much larger effects for patients who adhered to the intervention (-0.5 A1c change). Additionally, patients in both the treatment and control group of this intervention were assigned to quarterly office visits, with structured SMBG patients instructed to bring their readings to consult with their physician. Availability of this data encouraged primary care physicians to treat glycemia earlier, more frequently, and more effectively. Significantly more patients assigned to structured SMBG group received recommendations for a

treatment change as compared with control subjects. These findings highlight the key role that physician engagement with SMBG data plays in its effectiveness.

Nearly all randomized controlled trials of SMBG have had patients monitor their glucose using either pen and paper or store the information on the monitoring device itself to be brought to an office visit for physician viewing. As emphasized above, physicians play an important role in interpreting blood glucose trends, but likely do not have access to this patient generated data between office visits. Though technology to electronically transmit blood glucose readings is available, it is not widely used as a standard practice of care. The TELEDIAB-1 study piloted the Diabeo system (a smartphone coupled to a website) which incorporated automated advice on the insulin doses required; and remote monitoring by teleconsultation. Use of the system improved A1c by 0.9% vs controls in patients with chronic, poorly controlled type 1 diabetes (Charpentier et al 2011). However, there are few examples of integration of such technologies into Electronic Medical Records systems in a manner that would allow for wide-scale use. One study demonstrated the feasibility of automatically sending data from continuous glucose monitors to EMR patient portals for physician viewing, but did not test the impact of this on patient outcomes (Kumar et al 2016). To our knowledge, there is no randomized trial or prior research testing the causal effects of integrating of data from patient self blood glucose monitoring into EMRs on a wide-scale.

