2. **Learn how:** See [insert link to instructions/screenshots] to learn how to use the electronic blood glucose flowsheets on MyChart
3. **Link your devices:** You don't need to have special equipment to use the flowsheets, but if you have an Apple/iOS device and compatible glucometer, you can set up automatic data transfer. This will pull the results of your glucose tests into MyChart automatically, making it even easier to track. See [insert link to instructions] for help setting this up, and for a list of compatible devices.
4. **Track your blood glucose:** For the next 3 months, try to enter at least 6 measurements total per week, spread out over a few different days. However, don't be discouraged if you miss a day-- even tracking occasionally could be beneficial to your health.

Note: If you've never tested your blood glucose before, get in touch with [Practice Contact] to make sure you have all the materials and instructions you need, and to confirm that testing is right for you. Patients who think they might be pregnant should also be sure to talk to a physician before starting any new tracking regime.

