4.1 Sample Size

Non-pregnant adult patients of Inova primary care physicians with a current diabetes mellitus diagnosis and active MyChart account at time of treatment administration will be included in the study. The estimated number of patients is around 7200, from 71 primary care physicians across 24 selected Inova primary care practices.

Power Calculations

Power calculations were performed using the “clustersampsi” command in Stata. Knowledge of available sample and estimates/assumptions of control outcome mean, variance, and intraclass correlation were used to calculate a minimum detectable effect size for the key outcomes of flowsheet adoption (extensive margin, dichotomous rate of adoption) and changes in mean A1c.

Flowsheet Adoption: Practice Level Treatment-Control Comparison

Sample Size: 7200

Number of Treatment Arms: 2

Number of Clusters: 24

Assumed Control Adoption Rate: 2%

Assumed Intra-Cluster Correlation (within practices): 0.1

Minimum Detectable Effect: **9.5 percentage point increase in flowsheet orders**

Mean HbA1c: Practice Level Treatment Control Comparison

Sample Size: 7200

Number of Treatment Arms: 2

Number of Clusters: 24

Assumed Control HbA1c Mean: 6.74

Assumed Control HbA1c Standard Deviation: 1.39

Assumed Intra-Cluster Correlation (within practices): 0.07

Assumed Baseline Correlation: 0.80

ITT Minimum Detectable Effect: **0.27 change in A1c**

Flowsheet Adoption: Individual Level Comparison between Messaging Assignment Groups in Treatment Practices

Sample Size: 3600

Number of Arms (including no reminder): 4

Assumed No Reminder Adoption Rate: 20%

Minimum Detectable Effect: **5.5 percentage point increase in use of flowsheets when compared to no reminder**

Justification

The sample size represents the entire population of Inova primary care patients with diabetes who have active MyChart accounts and are therefore able to access the blood glucose tracking feature. The minimum detectable effects resulting from power calculations above are in-line with similar studies cited in the protocol background. Metastudy reviews of the effect of self monitoring of blood glucose found a 0.33 point change in A1c.

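### Baseline insulin use is neither adjusted for nor a planned comparison, which costs some precision, leaves a likely predictor uncontrolled in the surname-assigned reminder arms, and hides any A1c difference by insulin use

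*Combined protocol and SAP*

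**What the plan says.** **Population.** Section 4.1 takes non-pregnant adult primary care patients "with a current diabetes mellitus diagnosis and active MyChart account at time of treatment administration will be included in the study". Section 2.5 agrees, apart from excluding three named sites. Neither restricts by diabetes type or treatment, so insulin users and non-users are both in.

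**Background.** Section 1.3 separates the two groups. It states "For patients who are insulin-dependent, self monitoring of blood glucose (SMBG) is a critical aspect of disease management", and then that "for non-insulin dependent type 2 diabetics, there has been some debate over the value of self tracking". The meta-analytic A1c reductions it goes on to quote belong to that second discussion.

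**Intervention.** The launch message in Section 3.1.1 promotes testing as well as recording: "For the next 3 months, try to enter at least 6 measurements total per week, spread out over a few different days". It also tells patients "If you need help learning how to measure your blood glucose or getting testing supplies, you can contact" a practice contact. Under Section 3.2, control practices receive no encouragement.

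**Analysis.** Section 4.2 plans regressions without covariates and "a version controlling for patient age/gender, race/ethnicity, A1c at baseline, days since most recent office visit at baseline, and doctor fixed effects", plus a flag for participation in another study. Standard errors are clustered by practice for the practice-level contrasts. Sections 3.4 and 4.2 name no insulin, diabetes-type or prior-testing covariate, subgroup or interaction. Section 3.3 assigns reminders by the first letters of the surname, concedes that this is not fully random, and names race/ethnicity as the control for it.

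**The concern.** Insulin use plausibly predicts how many readings a patient has to enter and how often the medication list changes. Leaving it out has three consequences.

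- **Precision.** Variance in entries, adoption and medication changes that a baseline field could explain stays in the residual.
- **Reminder arms.** Practice randomisation protects the treatment–control contrast. It does not protect comparisons between surname groups, where any difference in insulin share goes straight into the adoption contrast unless it is adjusted for.
- **Heterogeneity.** The background gives a reason to expect different effects in the two groups, but the plan reports one pooled A1c effect. A null, or a modest benefit, could be an average of unlike results.

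**Working it through.** **Inputs from Section 4.1.** 7,200 patients in 24 practices, taken here as 12 per arm with 300 patients each; A1c SD 1.39, intra-cluster correlation (ICC) 0.07, baseline correlation 0.80; 3,600 patients in four reminder arms (900 each); 20% adoption without a reminder. Two-sided 5% and 80% power are assumed, since the plan states neither. The insulin share, adoption by insulin use and ICC of insulin use are not in the documents; every value for them below is an assumption.

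**1. The plan's own figures reproduce.**
- A1c: design effect = 1 + 299 × 0.07 = 21.93. SE = 1.39 × √(1 − 0.80²) × √(2 × 21.93/3600) = 0.0921. With t quantiles on 22 df, (2.074 + 0.858) × 0.0921 = 0.27, as stated.
- Reminders: (1.960 + 0.842) × √[(0.20 × 0.80 + 0.255 × 0.745)/900] = 0.055, as stated.

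The power figures are not at fault.

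**2. Adoption variance explained by insulin use, reminder comparison.** With insulin share s, adoption pI in users and pN in non-users, and overall adoption held at 20%: pN = (0.20 − s·pI)/(1 − s), and R² = s(1 − s)(pI − pN)²/(0.20 × 0.80). The adjusted MDE is about 5.5 × √(1 − R²).

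| s | pI | pN | gap | R² | MDE (points) |
|---|---|---|---|---|---|
| 0.30 | 0.35 | 0.136 | 0.214 | 0.060 | 5.3 |
| 0.25 | 0.40 | 0.133 | 0.267 | 0.083 | 5.3 |
| 0.20 | 0.50 | 0.125 | 0.375 | 0.141 | 5.1 |

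By the same gaps, each percentage point of difference in insulin share between two surname groups moves their adoption contrast by about 0.21 to 0.38 points.

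**3. Chance imbalance between practice arms.** With a 25% insulin share, the SD of the arm difference = √[2 × 0.25 × 0.75/3600 × (1 + 299 × ICC)]. That is 2.7, 4.1 and 5.7 percentage points at an ICC of 0.02, 0.05 and 0.10. Times the 0.267 gap, a one-SD imbalance moves adoption by about 0.7 to 1.5 points, against a practice-level MDE of 9.5. The gap would be smaller in control practices, where adoption is assumed to be 2%.

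**4. What a pooled A1c effect can hide.** A pooled effect of 0.27 fits 0.27 in both groups. It also fits 0 in insulin users and 0.27/(1 − s) in non-users: 0.34, 0.39 or 0.45 at s = 20%, 30% or 40%.

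**5. Precision of a split.** The step 1 formula is used with 300·s or 300·(1 − s) patients per practice, keeping SD, ICC and correlation unchanged. For s from 15% to 40%, the MDE is 0.30 to 0.28 in insulin users and 0.27 in non-users, because clustering dominates the variance. For the interaction it is about 0.15 to 0.11 if practice effects are common to both groups, and about 0.41 to 0.39 if they are independent.

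**The case against.** The strongest reply is that nothing here biases the main result. The A1c hypothesis (Sections 1.2.3 and 3.4) is already the ITT effect of promotion; practices are randomised; practice-level variation is inside the assumed ICC and the clustered errors; and baseline A1c, assumed to correlate 0.80 with the outcome, is already in the adjusted model. The reminder gain is only 0.2 to 0.4 points of MDE, and it rests on assumed inputs. All of this stands, and it limits the point to an improvement.

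A reader might infer more: that because insulin use is omitted, the A1c result cannot tell EHR integration from extra testing, and that insulin users, as patients who already test, would supply the evidence on integration. The documents do not support this.

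- The intervention bundles testing and recording. A covariate cannot separate the two parts.
- No baseline testing rate is given. Insulin users in treatment practices receive the same request to "try to enter at least 6 measurements total per week", so their testing may rise too, and some non-users may already test. A difference between the groups would be effect modification, not evidence of mechanism.
- A detectable fall arising wholly from new testing in non-users is also unlikely on these figures. With 75% non-users, 13.3% of them adopting, new testing confined to adopters and the 0.36 reduction in Section 1.3, pooled A1c moves 0.75 × 0.133 × 0.36 = 0.036. With the largest single-study effect quoted there, 0.69, it moves 0.07. Both are well below 0.27.
- The plan has some evidence on mechanism: messages, calls, visits, medication changes, and the contrast between the patient-value and doctor-value reminders. It is indirect.

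The residue is one of wording. Section 1.3 presents the gap as "testing the causal effects of integrating of data from patient self blood glucose monitoring into EMRs on a wide-scale", which is narrower than what the A1c contrast estimates.

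**Conclusion.** The point holds as a worthwhile, low-cost improvement and not as a threat to validity. The practice-level ITT effect of the promotion package is sound as designed. Omitting baseline insulin use gives up modest precision (reminder MDE 5.5 against about 5.3–5.1 points), leaves a likely predictor unadjusted where assignment is not random, and prevents the trial from showing a heterogeneity that its own background makes plausible. The precision figures rest on assumed insulin shares of 20–30% and adoption of 35–50% in users. That insulin use predicts entries and medication changes is an inference from Section 1.3, not a documented figure, and no size can be given for the gain on those two outcomes.

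**What to change.** 1. **Section 4.2, adjusted model.** Add baseline insulin use (yes/no), read from the medication list before the first practice contact, for all outcomes. For the practice-level contrast, specify a version in which the treatment effect is estimable: if each doctor works in a single practice, doctor fixed effects absorb a treatment assigned by practice. The documents do not say whether doctors work across practices.
2. **Sections 3.4 and 4.2, secondary analyses.** Pre-specify the A1c and entry-count ITT comparisons by baseline insulin use, with an arm-by-insulin interaction, before outcomes are seen.
3. **Section 3.4, interpretation.** State that the A1c contrast estimates promotion of testing plus electronic recording. Do not present it, or the insulin-user subgroup, as proof of an effect of EHR integration alone.

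**Cost.** One extra baseline field. The medication list is already needed to count alterations, although the documents do not say that baseline drug class is extracted. Subgroup estimates will be less precise than the pooled one (MDE 0.27–0.30 against 0.27), and the power of the interaction test is uncertain (MDE anywhere from 0.11 to 0.41), so a non-significant interaction should not be read as equal effects. Randomisation, intervention and sample size do not change.
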